2.4. Clinical Experience

Study 1 evaluated the efficacy of VOLTAREN® GEL for the treatment of osteoarthritis of the knee in a 12-week, randomized, double-blind, multicenter, placebo-controlled, parallel-group trial. VOLTAREN® GEL was administered at a dose of 4 g, 4 times daily, on 1 knee (16 g per day). Pain as assessed by the patients at Week 12 using the WOMAC (Western Ontario and McMaster Universities Osteoarthritis Index) Pain Sub index was lower in the VOLTAREN® GEL group than the placebo group.

Study 2 evaluated the efficacy of VOLTAREN® GEL for the treatment of osteoarthritis in subjects with osteoarthritis of the hand in an 8-week, randomized, double-blind, multicenter, placebo-controlled, parallel-group study. VOLTAREN® GEL was administered at a dose of 2 g per hand, 4 times daily, on both hands (16 g per day). Pain in the target hand as assessed by the patients at Weeks 4 and 6 on a visual analogue scale from 0 to 100 was lower in the VOLTAREN® GEL group than the placebo group.¹¹

Table 2: Efficacy outcomes of VOLTAREN® GEL in Studies 1 and 2

Efficacy outcomes of VOLTAREN® GEL in Studies 1 and 2				
		VOLTAREN® GEL	Placebo (Vehicle)	Adjusted Difference (Placebo - VOLTAREN® GEL)
Study 1 (Knee) WOMAC Pain * #	Sample Size	127	119	
	Mean Outcome	28	37	$\Delta = 7 \dagger$
	95% Confidence			(1, 12)

Efficacy outcomes of VOLTAREN® GEL in Studies 1 and 2				
		VOLTAREN® GEL	Placebo (Vehicle)	Adjusted Difference (Placebo - VOLTAREN® GEL)
at Week 12	Interval			
Study 2 (Hand) Pain Intensity # at Week 4	Sample Size	198	187	
	Mean Outcome	43	50	$\Delta = 7 \ddagger$
	95% Confidence Interval			(2, 12)
Study 2 (Hand) Pain Intensity # at Week 6	Sample Size	198	187	
	Mean Outcome	40	47	$\Delta = 7 \ddagger$
	95% Confidence Interval			(1, 13)

* WOMAC = Western Ontario McMaster Osteoarthritis Index.

Scale from 0 (best) to 100 (worst).

† Difference is adjusted using an analysis of covariance (ANCOVA) model with main effects of treatment and center and baseline covariate.

‡ Difference is adjusted using an analysis of covariance (ANCOVA) model with main effects of treatment, center, and indicator of pain in the CMC-1 joint, and baseline as a covariate, and the treatment-by-CMC-1 strata.

2.5. Contraindications

- Known hypersensitivity (e.g., anaphylactic reactions and serious skin reactions) to diclofenac or any components of the drug product¹¹
- History of asthma, urticaria, or other allergic-type reactions after taking aspirin or other NSAIDs. Severe, sometimes fatal, anaphylactic reactions to NSAIDs have been reported in such patients¹¹
- In the setting of coronary artery bypass graft (CABG) surgery¹¹

2.6. Study Rationale

This is a study designed to evaluate the therapeutic equivalence and safety of a Diclofenac Sodium Gel in order to facilitate registration of a generic version of Diclofenac Sodium Gel, 1% of Mylan Inc. The Reference Listed Drug (RLD) is Voltaren® Gel (Diclofenac Sodium Topical Gel) 1%. This study will be conducted in male and female subjects with confirmed diagnosis of osteoarthritis of the knee.

2.7. Dosage & Administration

Knee

The proper amount of Diclofenac Sodium Gel should be measured using the dosing card. The dosing card should be used for each application of drug product. The gel should be applied within the rectangular area of the dosing card up to 4 gm line. The dosing card provided with the product can be used to apply the gel. The hands should then be used to gently rub the gel into the skin. After using the dosing card, hold with fingertips, rinse, and dry.

2.8. Risks and Benefits

Mylan [REDACTED] has developed the generic formulation of Diclofenac Sodium Gel, 1% which may or may not be effective.

Most common adverse reactions (incidence >2% of patients treated with VOLTAREN® GEL and greater than placebo) are application site reactions, including dermatitis.

Application site reaction reported with diclofenac gel includes: application site dermatitis, application site pruritus, application site erythema, application site paresthesia, application site dryness, application site vesicles, application site irritation and application site papules.¹¹

Other adverse reactions includes cardiovascular thrombotic events, GI bleeding, ulceration and perforation, hepatotoxicity, hypertension, heart failure, and edema, renal toxicity and hyperkalemia, anaphylactic reactions, serious skin reactions and hematologic toxicity. Potential benefits include improvement in pain, stiffness and improved physical function associated with OA.

2.9. Non-Investigational Medicinal Products (NIMP)/Rescue Medication – Acetaminophen (paracetamol):

Use¹²:

- Temporarily relieves minor aches and pain due to:
 - Minor pain of arthritis
 - Muscular aches
 - Backache
 - Pre- menstrual and menstrual pain
 - Common cold
 - Headache
 - Toothache
- Temporarily reduces fever

Warnings

Hepatic Effects¹²:

- Severe liver damage may occur if patient will take
 - more than 4,000 mg of acetaminophen (paracetamol) in 24 hours with other drugs containing acetaminophen (paracetamol)
 - 3 or more alcoholic drinks every day while using this product

- Subjects with allergy to acetaminophen (paracetamol)

3. OBJECTIVES

Primary Objectives:

1. To determine the clinical equivalence of Test Drug(Diclofenac sodium gel of 1% of Mylan Inc.) with the Reference Listed Drug (RLD)(Voltaren® Gel 1% of Novartis Consumer Health, Inc.) as measured by mean change from baseline in the Western Ontario and McMaster Universities Osteoarthritis Index (WOMAC) Likert (version 3.1) pain score.
2. To establish superiority of the Test Drug and Reference Listed Drug (RLD) over placebo in mean change from baseline in the WOMAC Likert (version 3.1) pain score.

Secondary Objectives:

1. To assess the safety and tolerability of study treatments.
2. To determine the clinical equivalence of Test Drug(Diclofenac Sodium gel) with the Reference Listed Drug (RLD)(Voltaren® Gel) as measured by mean change from baseline in subjects whose baseline WOMAC Likert (version 3.1) pain scores are less than or equal to 10.

4. STUDY DESIGN

Randomized, Double-blind, Multi-centric, Parallel, Active and Placebo Controlled, Three Arm, Clinical Study, with subjects randomized in the ratio of 1:1:1 of Mylan's Diclofenac Sodium Topical Gel 1%, Voltaren® Gel 1% (Reference Listed Drug), and Placebo gel respectively.

4.1. Study Overview

This is a double-blind, multiple-site, randomized, parallel-design study to investigate the bioequivalence with clinical endpoint of Mylan's Diclofenac Sodium Topical Gel, 1% to Voltaren® Gel, 1% (Novartis US) and to investigate that both the active products are superior to placebo.

Subjects will have to visit the clinic for the following visits during the study –

[figure not shown]
Visit 1 – Screening visit (within 28 days prior to randomization)

Visit 2 – Start of Placebo Run-in period (Day -11 to Day -7)

Visit 3 – Randomization (baseline) visit (Day 0)

Visit 4 – Interim visit (Week 2/Day 14 ± 4)

Visit 5 – End of study (Week 4/Day 28 ± 4)/ Early termination visit

Figure 1: Study Design Flow Chart

WOMAC - Western Ontario and McMaster Universities Arthritis Index, POM - Pain on Movement

* Telephonic contact in midway for well-being, concomitant medication and treatment compliance

** Telephonic contact to stop usage of rescue medication for 3 days prior to clinic visit

After informed consent process and completion of all screening assessments, the eligible subjects will be requested to stop the currently ongoing osteoarthritis drug therapy. The wash out period (run-in period) of 7 days or \geq 5 half-life of previous osteoarthritis drug therapy, whichever is longer, will be maintained before the baseline visit. Subjects will undergo at least 7 days of placebo run-in period. In case subject extends run-in period beyond 11 days, continuation of the subject will be decided in consultation with Medical monitor.

The Pain on Movement (POM) score on a Visual Analog Scale (VAS) and Western Ontario and McMaster Universities Osteoarthritis Index (WOMAC Likert version 3.1) pain score will be recorded at the start of run-in Period and at the end of run-in Period (i.e. immediately prior to randomization on the day of baseline visit). Recording of the VAS will be done for both the knees and recording of the WOMAC pain score will be done for the target knee.

During the washout period, subjects will undergo a single-blind placebo run-in period where the subjects will not be aware of the placebo nature of the drug. Subjects will be provided with placebo gel for the administration. Approximately 4 gm dose of placebo gel will be applied to the target knee four times daily for at least 7 days. Target knee means the knee which is more painful will be identified during the screening visit. First administration of gel will be done at the study site.

At baseline visit, subjects will be randomly assigned in 1:1:1 ratio to Mylan's Diclofenac Sodium Topical Gel 1%, Voltaren® Gel 1% (Reference Listed Drug) and Placebo. All the subjects will be instructed to apply the gel next day (Day 1) onwards. All subjects will be applying approximately 4 gm dose of either Mylan's Diclofenac Sodium Topical Gel 1% or Reference Listed Drug (RLD) or Placebo gel to the arthritic target knee four times daily for 4 weeks.

The Western Ontario and McMaster Universities Osteoarthritis Index (WOMAC Likert version 3.1) pain score for the target knee and pain on movement (POM) on a Visual Analog Scale (VAS) for both the knees will be recorded on Week 2 and Week 4 from the start of the treatment.

Acetaminophen (paracetamol) tablets will be given to the subjects for use as a rescue medication or for the treatment of aches and pains unrelated to knee pain such as headache during treatment period (except 3 days prior to Visit 4 and Visit 5). Maximum allowed dose of acetaminophen (paracetamol) will be 2 gm/day. Consumption of rescue medications in terms of number of tablets consumed will be monitored.

Subject diary will be provided to subjects to record study medication gel application, rescue medication, side effects, and concomitant medication details. Subjects will be trained regarding how to use the subject diary. Subject diary will be used to evaluate drug application compliance. Subjects will be trained via a detailed and translated instruction subject diary on how to administer the study drug.

Physical examination will be conducted during each visit (except at the start of run-in period visit). Application site reaction assessment will be conducted on each visit after start of run-in period.

A standard 12-lead ECG will be recorded after 5 minutes of rest in the supine position on screening visit and on end of study visit. Vital signs will be measured after 5 minutes of rest (sitting) on each visit.

Serum pregnancy test for females of childbearing potential will be performed at screening and end of treatment visit. The urine pregnancy test can be performed if clinically indicated during other visits. If urine pregnancy is found to be positive, serum pregnancy will be drawn and analyzed for

confirmation. If serum pregnancy test will found positive then patient will be excluded from the study and followed up.

Laboratory assessments like hematology and biochemistry will be performed during screening and end of study. The hematology and biochemistry at screening to be performed within 14 days of baseline visit. If the gap between lab assessments and baseline visit will be more than 14 days, the lab assessments will be repeated at baseline visit. Laboratory investigations (if clinically significant) can be repeated once as per investigator's discretion.

Principal investigator or designee will contact the subjects approximately midway between the visit 3-4 and visit 4-5 for assessment of the well-being, adverse event, concomitant medication, and treatment compliance.

Additional telephonic contact to reiterate the instructions regarding the use of rescue medications during 3 days prior to visits 4 and 5 will be done. Use of rescue medications by subjects during this period for intolerable pain will require rescheduling the visits in such a way that visits happen after at least 3 days of stopping rescue medication and subjects will be required to inform the site about the rescue medication use. The same will be documented in the source notes.

Statistical analysis will be done as per the [Section 12.0](#).

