5.2. Exclusion Criteria

1. Pregnant or lactating or planning to become pregnant during the study period.
2. X-ray showing evidence of OA with Kellgren-Lawrence grade 4 disease.
3. History of OA pain in the contralateral knee requiring medication (OTC or prescription) within 1 year prior to screening.
4. After discontinuing all pain medications (placebo run-in period) for at least 7 days, had a baseline score of ≥ 20 mm on a 0-100 mm Visual Analog Scale (VAS) for the contralateral knee immediately prior to randomization.
5. History of OA of either Hip or Hands
6. History of secondary OA (e.g. congenital, traumatic, gouty arthritis), rheumatoid arthritis.
7. History of chronic inflammatory disease (e.g., colitis) or fibromyalgia.
8. History of Drugs or Alcohol abuse within the previous year.
9. Symptomatic peripheral vascular disease of the study leg (prior or current).
10. Any musculoskeletal condition that would impede measurement of efficacy at the target knee.
11. History of regular headaches or backache which warrants often use of acetaminophen (paracetamol) within the previous year.

12. Concomitant skin disease at the application site which may affect study drug application or tolerability evaluation.
13. History of active asthma within the previous year that may require periodic treatment with systemic steroids during the study period (note: inhaled steroids for this condition are allowed).
14. History of aspirin sensitive asthma.
15. History of uncontrolled hypertension (blood pressure more than 150/100 mm of Hg) in spite of treatment within the previous year.
16. History of myocardial infarction, thrombotic events, stroke, congestive heart failure, impaired renal function (Serum creatinine $> 1.5 \times$ ULN) or liver disease within the previous year.
17. History of coronary artery bypass graft within 6 months of screening.
18. History of gastrointestinal bleeding or peptic ulcer disease in last one year.
19. Known allergy to aspirin, nonsteroidal anti-inflammatory drugs (NSAID) or acetaminophen (paracetamol).
20. Elevated transaminases (≥ 3 times ULN) and Hemoglobin < 9.0 g/dL at screening.
21. Viscosupplementation in any joint including the target knee within 6 months prior to screening
22. Receiving physical therapy (at an outpatient/clinic setting) for the lower extremities or having received physical therapy for the lower extremities within 1 month before screening.

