9.6 Pregnancy Test

Serum Pregnancy Test for females of childbearing potential will be performed during screening visit and at the end of study or early termination visit. The urine pregnancy test can be performed if clinically indicated during other visits. If urine pregnancy is found to be positive, serum pregnancy will be done for confirmation. If serum pregnancy test will found positive then patient will be excluded from the study and followed up.

Acceptable forms of contraception include the following:

- Oral Contraceptives or Intrauterine Device in place for at least 3 months prior to the start of the study and remaining in place during the study period, or
- Double Barrier methods containing or used in conjunction with a spermicidal agent, or
- Contraceptive Patches/ Implants, or
- Abstinence: Subjects who will be practicing abstinence will agree to have a documented second acceptable method of birth control if the subject become sexually active during the course of her study participation.

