10.3 Treatment Period Visits

10.3.1 Visit 3 (Baseline): Day 0

The following procedures will be performed at the Randomization Visit:

- **Physical Examination and Vital Signs**
- **Inclusion/Exclusion Criteria Review**
- **Urine Pregnancy Test** (for all females of childbearing potential) if clinically indicated.
- **Laboratory investigations** (if not performed within 14 days of baseline visit)
- **Pain on Movement (POM)** assessment in both the knees- 100mm VAS
- **WOMAC pain score assessment of the target knee**
- **Subject diary (placebo run-in period) review and its collection**
- **Assessment of treatment compliance**
- **Application site reaction assessment**
- **Study medication and Subject diary for treatment period dispensing:** Study medication for treatment period will be dispensed by the site staff to qualified subjects. A subject diary, containing instructions for subjects, will be dispensed to each qualified subject.
- **Instructions on study medication application and Storage**
- **Collection of the unused IP dispensing during placebo run-in period**
- **Rescue medication dispensing**
- **Assess Adverse Events**
- **Assessment of Concomitant Medications**

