a A physical examination includes the evaluation of general appearance, eyes, head and neck, abdomen, lymph nodes, skin, cardiovascular system, respiratory system, and musculoskeletal system.

b A standard 12-lead ECG will be recorded after 5 minutes of rest in the supine position.

c Evidence of osteoarthritis with Kellgren-Lawrence grade 1-3 disease. X-ray of target knee will be performed on screening if not performed for more than 1 year prior to baseline.

d Vital signs will be measured by the investigator or designee after 5 minutes of rest (sitting).

e Pregnancy test is only required for females of childbearing potential. Serum pregnancy to be performed at screening and end of treatment visit.

f The urine pregnancy test can be performed if clinically indicated. If urine pregnancy is found to be positive, serum pregnancy will be done for confirmation.

g All hematology and clinical chemistry laboratory assessments are to be conducted preferably in a fasted state.

h The hematology and biochemistry (lab assessments) at screening to be performed within 14 days of baseline visit. If the gap between lab assessments and baseline visit is more than 14 days, the lab assessments should be repeated at baseline visit.

i WOMAC pain score (pain score = 0 to 20), will be determined by the subject's responses to five questions (S1–S5) using a 5-point Likert scale (i.e.,

‘none’=0; ‘mild’=1, ‘moderate’=2; ‘severe’=3; ‘extreme’=4). The questions pertain to the amount of pain the subject is currently experiencing in the target knee [i.e., ‘How much pain do you have’ when ‘Walking on a flat surface’ (S1), ‘Going up or down stairs’ (S2), ‘At night while in bed’ (S3), ‘Sitting or lying’ (S4), ‘Standing upright’ (S5)]

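### The last mandatory pregnancy test before randomization can be 28 days old, because the urine test listed at Visit 3 is done only if clinically indicated

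*Protocol*

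**What the plan says.** Pregnancy bars entry. Inclusion 1 admits only non-pregnant females, and exclusion 1 reads "Pregnant or lactating or planning to become pregnant during the study period". Protocol 10.2 and 10.3.1 list a review of the criteria at Visit 2 and again at Visit 3.

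The mandatory tests are two serum tests. Protocol 4.1 says "Serum pregnancy test for females of childbearing potential will be performed at screening and end of treatment visit", and Protocol 9.6 says "Serum Pregnancy Test for females of childbearing potential will be performed during screening visit and at the end of study or early termination visit". Timing follows from the visit list in 4.1: "Visit 1 – Screening visit (within 28 days prior to randomization".

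Between those two tests, urine testing is conditional. Protocol 4.1 says "The urine pregnancy test can be performed if clinically indicated during other visits". The Visit 3 entry in Protocol 10.3.1 carries the same qualifier, "for all females of childbearing potential) if clinically indicated", as do the entries for Visits 2 and 4. In the SAP 11.1 schedule, Visits 2, 3 and 4 share footnote f, which reads: "The urine pregnancy test can be performed if clinically indicated. If urine pregnancy is found to be positive, serum pregnancy will be done for confirmation".

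Randomized gel starts the day after Visit 3: "All the subjects will be instructed to apply the gel next day (Day 1) onwards".

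**The concern.** The eligibility check at Visit 3 is the last one before a subject may receive active drug, since the run-in gel is placebo. The pain criteria are measured at that visit, immediately before randomization. Pregnancy status need not be: unless something prompts a urine test, the site confirms exclusion 1 from the screening result.

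A negative serum test at screening does not exclude a conception after it, or one too recent for it to detect. A woman who is pregnant at Visit 3 without anyone suspecting it could then be randomized, with a two-in-three chance of an active arm. That would be an avoidable exposure in pregnancy, an event that Protocol 11.3 takes seriously enough to require reporting within 24 hours and updates at least every 3 months until birth or termination. She would also be a randomized subject who did not meet the entry criteria.

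**Working it through.** No sample size, power or error-rate figure in the plan bears on this point. The check is a comparison of the passages and a count of days.

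**Agreement between passages.** The synopsis, Protocol 4.1, 9.6 and 10.1 to 10.3, and SAP 3.1 and 11.1 all give the same scheme: serum tests at Visits 1 and 5, urine tests at Visits 2 to 4 only when indicated. The Protocol's own schedule (Appendix II) is not in the text available for this review.

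**Age of the last mandatory result.**
- Longest, at randomization: Day -28 to Day 0 = 28 days.
- Longest, at first randomized application: Day -28 to Day 1 = 29 days.
- Shortest, at randomization: the SAP 11.1 schedule note allows screening and run-in start on the same day, and run-in lasts at least 7 days, so about 7 days.

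**Comparison with the plan's other recency rule.** Protocol 4.1 and 9.5 require hematology and biochemistry to be repeated at baseline when more than 14 days old. The pregnancy test is not in the 9.5 list. The longest permitted age of a pregnancy result is thus 28 / 14 = 2 times the limit for those tests.

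**Size of the remaining gap.** The documents give neither the share of women of childbearing potential nor a contraceptive failure rate. As an illustration only, assume that 5% to 20% of the 1212 randomized subjects are of childbearing potential, that annual contraceptive failure is 1% to 10%, and that every gap is the full 28 days. Expected conceptions between screening and randomization = 1212 × share × annual rate × 28/365.
- Low: 1212 × 0.05 × 0.01 × 28/365 = 60.6 × 0.01 × 0.0767 = about 0.05.
- High: 1212 × 0.20 × 0.10 × 28/365 = 242.4 × 0.10 × 0.0767 = about 1.9.

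With 1:1:1 allocation, two thirds would fall in active arms: about 0.03 to 1.2. Shorter gaps lower these figures, and some conceptions would be too recent for a Visit 3 test to detect. Conceptions already present but undetectable at screening are not counted and would add to them.

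**Effect on the analysis sets.** SAP 6.5 and 6.6 require all entry criteria to be met for the mITT and PP populations. Even at the high end, 1.9 / 1212 = about 0.16% of randomized subjects would be affected. Each arm has 404 - 363 = 41 subjects above the number stated for superiority, so power is not at issue.

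**The case against.** The strongest objection is that other safeguards already stand in the way. Inclusion 10 requires women to be postmenopausal, surgically sterile or using a listed contraceptive method; exclusion 1 also bars women who plan a pregnancy; criteria are reviewed at Visits 2 and 3; a urine test may be done whenever indicated; and pregnancy leads to withdrawal (Protocol 7.7). This stands in large part. A known or suspected pregnancy would be caught. It does not close the gap, because contraception can fail, the 3-month lead-in applies only to oral contraceptives and intrauterine devices, and withdrawal acts only after detection.

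A second objection is that clinical indication is undefined and may well include a missed period or a reported contraceptive lapse. This also stands. A reader might infer that no woman without symptoms would be tested, or that a pregnancy could surface only at Visit 5. The documents do not support that: Visit 4 and the two midway telephone contacts offer earlier opportunities.

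Third, the 14-day rule for laboratory tests has another possible purpose. SAP 7.12.5 uses those tests as the baseline for change and shift tables. The comparison shows that the plan has a recency rule it could have applied here; it does not show that the sponsor regards a 28-day pregnancy result as too old.

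Fourth, systemic exposure from 4 g four times daily is low: Protocol Table 1 gives 5.8% of oral AUC and 0.6% of oral Cmax. This limits the weight of the point but does not make an exposure barred by the entry criteria acceptable.

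**Conclusion.** The gap is real and small. The last mandatory pregnancy test before randomization can be up to 28 days old (about 7 days at the shortest), and the plan does not require the Visit 3 eligibility review to be backed by a current one. What is left after the existing safeguards is an unsuspected pregnancy present at randomization, probably in very few subjects. The range of 0.05 to 1.9 rests on assumed shares and failure rates, not on figures in the documents.

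Three stronger readings are not supported. A reader might infer that the exclusion depends on the screening test alone; inclusion 10 and the repeated criteria review show otherwise. A reader might point to the 28 + 32 = 60 days that can separate the two mandatory tests (Day -28 to Day 32); most of that interval follows randomization and is not an eligibility question, and a test at Visit 3 would not detect later conceptions. A reader might infer a threat to the mITT or PP analyses; the number of subjects is negligible, and sample size, power and type I error are untouched. Nor do the pregnancy-testing passages contradict one another. They are consistent, but they leave an entry criterion without a current check at the visit where it is reviewed.

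The change is worth making for participant safety and for verification of eligibility.

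**What to change.** Align the pregnancy-testing passages with the Visit 3 eligibility review:

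1. In Protocol 10.3.1, remove the condition from the urine test already listed, so that every female of childbearing potential has a negative result before randomization. The existing serum confirmation of a positive result stays.
2. In SAP 11.1, give the Visit 3 cell of the pregnancy-test row its own footnote stating that the test is required. Keep footnote f for Visits 2 and 4. Editing footnote f itself would change all three visits.
3. Revise the sentence on other visits in the synopsis, Protocol 4.1, Protocol 9.6 and SAP 3.1 so that it excepts Visit 3. Without this, the edit would create contradictions that do not exist now. Check Protocol Appendix II for the same wording.

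The cost is one urine test per woman of childbearing potential, plus the wording changes. A positive urine result would occasionally delay randomization for serum confirmation. If that result is then negative, the POM and WOMAC assessments, which must immediately precede randomization, may need repeating, and a run-in extended beyond 11 days already requires consultation with the medical monitor. The change does not cover pregnancies too early to detect at Visit 3 or those that begin after it.
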